### **13.8 Termination or Interruption of Part or All of the Trial**

#### **13.8.1 Termination or Interruption of the Trial at Individual Trial Sites**

- 1) In the event of termination or interruption of the trial, the investigator will promptly provide the head of the trial site with written notification and a written explanation of the details of the termination or interruption of the trial.
- 2) When the sponsor has been informed by the head of a trial site that the investigator has terminated or interrupted the trial, the sponsor will obtain a detailed written explanation of the termination or interruption of the trial from the head of the trial site.

#### **13.8.2 Termination or Interruption of the Entire Trial**

- 1) When the entire trial is to be terminated or interrupted by the sponsor, the sponsor will promptly provide the heads of all trial sites involved in the trial and the

regulatory authority with written notification and a detailed written explanation of the reason for the termination or interruption of the trial.

- 2) When the investigator has received notification of termination or interruption of the entire trial by the sponsor from the head of the trial site, the investigator will obtain a detailed written explanation of the termination or interruption of the trial from the head of the trial site, promptly notify the trial subjects currently receiving IMP administration, and take necessary measures such as switching to appropriate alternative treatment(s).
- 3) When development of the IMP is terminated by the sponsor, the sponsor will promptly provide the heads and the investigators of all trial sites involved in the trial and the regulatory authority with written notification and a detailed written explanation of the reason for the termination of development.

### **13.9 Protection of Subjects' Personal Information**

In completion and handling of CRFs, the investigator and subinvestigator will take adequate care to ensure protection of the personal information of subjects. Individual subjects will be identified by subject numbers and subject identification codes. The sponsor will not provide the information obtained to any third party.

### **13.10 Compensation for Injury to Health**

Trial subjects will be compensated for health damages according to the criteria established by the trial sponsor with reference to the "Guidelines for Health Damage Compensation to Trial Subjects" (revised 25 Nov 2009) of the Japan Pharmaceutical Industry Legal Affairs Association. Compensation for this trial will comprise medical costs and medical benefits.

### **13.11 Agreement on Publication**

The sponsor may use the findings obtained from this trial for purposes such as an "Application for Approval of a Pharmaceutical Product" for the IMP.

When the results of this trial and relevant data are to be published in scientific journals or at academic meetings, the investigator will obtain prior written approval from the sponsor.

## **14 Trial Administrative Structure**

The administrative structure of this trial is shown in Annex 1, Annex 2, and Annex 3.

## 15 Scheduled Duration of the Trial

Overall trial duration: 01 Oct 2014 to 31 Dec 2019

- 1) Cohorts 1, 2, and 4  
(Primary Evaluation Part [Cohorts 1, 2, and 4])  
01 Oct 2014 to 31 May 2016  
(Extended Treatment Part [Cohorts 1, 2, and 4])  
01 Jun 2016 to 31 Dec 2019
- 2) Cohort 3  
(Primary Evaluation Part [Cohort 3])  
01 Sep 2016 to 30 Nov 2017  
(Extended Treatment Part [Cohort 3])  
01 Dec 2017 to 31 Dec 2019

10.3	Overall Survival	23
10.4	Adjustment for Covariates	23
10.5	Subgroup Analysis.....	23
11	Pharmacodynamic Analysis	24
11.1	DNA Methylation Inhibition.....	24
12	Rationale for Target Number of Subjects.....	25
13	Changes From Analyses Planned in the Protocol	26
14	References	27
15	Revision History	28

List of Abbreviations and Definition of Terms

List of Abbreviations

Abbreviation	Expansion
AE	Adverse event
ALT	Alanine aminotransferase
AML	Acute myeloid leukemia
AMLSG	Acute myeloid leukemia study group
AST	Aspartate aminotransferase
ATC	Anatomical Therapeutic Chemical
Cr	Creatinine
CR	Complete remission
CRi	Complete remission with incomplete blood count recovery
CRp	Complete remission with incomplete platelet recovery
CTCAE	Common Terminology Criteria for Adverse Events
DLT	Dose limiting toxicity
DNA	Deoxyribonucleic acid
ECG	Electrocardiogram, electrocardiography
ECOG	Eastern Cooperative Oncology Group
IMP	Investigational medicinal product
LINE-1	Long interspersed nucleotide element-1
MedDRA	Medical Dictionary for Regulatory Activities
MTD	Maximum tolerated dose
NCCN	National Comprehensive Cancer Network
NE	Not evaluable
PD	Pharmacodynamic(s)
PK	Pharmacokinetic(s)
PR	Partial response
PS	Performance status
PT	Preferred term
QTcF interval	QT interval as corrected by Fridericia's formula
RBC	Red blood cell
SAP	Statistical analysis plan
SD	Standard deviation
SOC	System organ class
TEAE	Treatment-emergent adverse event
WHO-DD	World Health Organization Drug Dictionary

1 Introduction

This statistical analysis plan (SAP) describes the methods of summary/analysis or assessment of the data collected in this trial. This SAP was prepared based on protocol version 8 (Protocol No.: 343-14-001) prepared on 13 Oct 2017.

The analysis methods for the pharmacokinetic (PK) evaluation are not described in this SAP, as a PK analysis plan will be prepared as a separate document. By-subject listings are not included in this SAP unless stated otherwise.

2 Trial Objectives

Primary objective:

To evaluate the tolerability of SGI-110 when administered subcutaneously to Japanese patients with acute myeloid leukemia (AML)

Secondary objectives:

- To perform PK evaluation of plasma SGI-110 and decitabine
- To evaluate efficacy (complete remission rate, composite complete remission rate, overall remission rate, overall survival, composite complete remission duration)
- To evaluate safety through observed adverse events (AEs) and examinations

Exploratory objective:

To perform pharmacodynamics (PD) evaluation of the extent of deoxyribonucleic acid (DNA) hypomethylation

3 Trial Design

This is a phase 1, multicenter, open-label study to evaluate the tolerability of SGI-110 in Japanese patients with relapsed or refractory AML after undergoing standard therapy or Japanese patients with AML aged 65 years or older who are not eligible for standard chemotherapy.

This trial consists of a screening period, dose limiting toxicity (DLT) evaluation period, and withdrawal examination. Subjects who complete investigational medicinal product (IMP) administration and all observations during the DLT evaluation period, and who do not have any apparent progression of AML, will be permitted to continue treatment with IMP following the DLT evaluation period if they wish. The primary evaluation data for Cohorts 1, 2, and 4 will have a cut-off date of 31 May 2016 and the primary evaluation data for Cohort 3 will have a cut-off date of 30 Nov 2017. The period up until the data cut-off will be defined as the primary evaluation part. This will be followed by an extended treatment part to assess long-term safety, which will include those subjects on IMP treatment who have consented to participate in the extended treatment part. Transition from the primary evaluation part to the extended treatment part will take place at the start of the next course after the data cut-off.

Administration of the IMP will be started in Cohort 1 (36 mg/m² in 5-day regimen) and 3 subjects will receive the IMP in this cohort. If none of the 3 subjects has a DLT during the DLT evaluation period, the study will proceed to the next cohort. If one of the 3 subjects experiences a DLT, 3 additional subjects will be enrolled and DLTs will be evaluated in a total of 6 subjects. The study will proceed to the next cohort only if no more than one of the 6 subjects has a DLT. If the number of subjects exhibiting a DLT within a cohort is $\geq 2/3$ or $\geq 2/6$, there will be no dose escalation.

In Cohort 2 (60 mg/m² in 5-day regimen) and Cohort 4 (90 mg/m² in 5-day regimen), DLTs will be assessed in the same manner. However, even if none of the first 3 subjects enrolled has a DLT, a total of 6 subjects will be enrolled in each of Cohorts 2 and 3 of which the dose has been determined as the recommended dose for a next phase study.

Based on the occurrence of DLTs, the tolerability at the recommended dose for a next phase study will be confirmed in Japanese subjects as well.

The sponsor will review safety data obtained from the previous cohort(s) and judge the transition to the next cohort, including selection of a cohort to proceed to, based on the advice of the Independent Data Monitoring Committee.

If the number of subjects exhibiting DLT within a cohort is $\geq 2/3$ or $\geq 2/6$, then there will be no transition to the next cohort, and the maximum tolerated dose (MTD) will be determined as follows:

$\geq 2/3$ or $\geq 2/6$ subjects with DLT	MTD
In Cohort 1	$< 36 \text{ mg/m}^2$ in 5-day regimen
In Cohort 2	36 mg/m^2 in 5-day regimen
In Cohort 4	60 mg/m^2 in 5-day regimen

If the incidence of DLT does not reach either $\geq 2/3$ or $\geq 2/6$ in any of the cohorts in the table above, the MTD will not be determined in this study. For Cohort 3 (60 mg/m^2 in 10-day regimen), DLT will be evaluated but the MTD of 10-day regimen will not be determined from the incidence of DLT.

The DLT evaluation period will be from the start of administration in Course 1 to the examination scheduled for Day 29 of Course 1. However, for subjects who have postponed the start of IMP administration scheduled for Day 1 of Course 2 (extended treatment period), the DLT evaluation period will last until the start of IMP administration in Course 2.

Subjects will be hospitalized for treatment during Course 1. Subjects will be required to remain hospitalized until the examination scheduled for Day 29 of Course 1 if they complete the trial in Course 1 (until the withdrawal examination if they are withdrawn during Course 1) and until the start of IMP administration in Course 2 if they proceed to the extended treatment period of Course 2 and the subsequent courses.

Dose-limiting toxicity shall be defined as any of the following AEs occurring during Course 1 for which there is a reasonable probability or possibility of a causal relationship with the IMP (being related to the IMP) if it cannot be reasonably explained by underlying disease, intercurrent illness, or concomitant medications. The severity of AEs will be graded in accordance with Common Terminology Criteria for Adverse Events (CTCAE) version 4.0.

- Non-hematologic toxicity of Grade 3 or higher, except for the following:
 - Nausea, vomiting, or diarrhea of Grade 3 that is controllable by optimal therapy
 - Grade 3 laboratory findings other than serum creatinine (Cr), bilirubin, aspartate aminotransferase (AST), or alanine aminotransferase (ALT), that are not associated with clinical manifestations
- Grade 4 thrombocytopenia that was not present at study entry and that is not resolved within 7 days

- Grade 4 neutropenia that was not present at study entry and that is not resolved within 7 days
 - Febrile neutropenia^{*}
If the febrile neutropenia is not resolved or improved during the DLT evaluation period, it shall be defined as DLT. If the febrile neutropenia is resolved or improved during the DLT evaluation period, it shall be judged whether it is defined as DLT based on the background of the subject and through consultation with the Independent Data Monitoring Committee.
 - Any AE that results in a delay of > 4 weeks in starting the next treatment course
- ^{*}In this trial, febrile neutropenia is defined as a neutrophil count of < 500/ μ L accompanied by a fever of $\geq 38^{\circ}\text{C}$

The DLT evaluation period will be for the duration of Course 1. Subjects who complete IMP administration and all observations during the DLT evaluation period, and who do not have any apparent progression of AML, will be permitted to continue treatment with IMP following the DLT evaluation period if they wish.

4 Implementation of Planned Analyses

One interim analysis for cohort 1, 2 and 4 of this study will be take place that the data will be locked on 25Aug2017. And one final analysis for cohort 1, 2, 3 and 4 of this study will take place for final locked.

SAP will be fixed before lock of database.

After confirmation of which subjects are to be included in the statistical analyses and how to handle the data in the statistical analyses and discussion of how to deal with problems unexpected at the time of planning, final analysis will be done based on the SAP by using the final data.

5 Statistical Analysis Sets

5.1.1 Safety Analysis Set

The safety analysis set will include subjects who have received at least one dose of the IMP.

5.1.1.1 Dose-limiting Toxicity Analysis Set

The DLT analysis set will include subjects in whom tolerability has been assessed in Cohorts 1 to 4 (subjects who have received all doses and completed all assessments scheduled for the DLT evaluation period).

5.1.2 Efficacy Analysis Set

The efficacy analysis set will include subjects who have received at least one dose of the IMP and have data of the efficacy endpoints after the start of IMP administration.

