### **3.3.2 Efficacy Endpoints (Primary Evaluation Part)**

Complete remission rate (CR), composite complete remission rate (CR + CRi + CRp), overall remission rate (CR + CRi + CRp + partial response [PR]), overall survival, and composite complete remission duration

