### 7.2.3.2 Outcome of Survival

The survival of each subject will be investigated at the end of the primary evaluation part of the trial (see [Section 15](#) Scheduled Duration of the Trial) and recorded in the CRF.

The date of survival confirmation will be recorded in the CRF if the subject is alive, the date of death and its reason if the subject has died, and the date of final survival confirmation if it is unknown whether the subject is alive.

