### **11.2 Handling of Data**

- 1) Acceptable time windows of timepoints for examinations  
The acceptable time windows of timepoints for examinations to be used in tabulation are detailed in the statistical analysis plan.
- 2) Handling of missing data  
How to handle missing data is described in the statistical analysis plan.
- 3) Handling of events and censoring  
In the analysis of overall survival, all deaths (regardless of cause) will be defined as events, and time to death from the start date of IMP administration will be analyzed. If subjects are alive at the end of the primary evaluation part, they will be censored (the day of survival confirmation will be the day of censoring).

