6.2.7 Overall Survival

Overall survival is defined as the number of days from the day the subject received the first dose of IMP to the date of death (regardless of cause).

Survival time will be censored on the last date of survival confirmation if a subject is alive or lost to follow-up.

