7.2 Statistical Analysis Sets

The frequency distribution of subjects included or excluded in each analysis set will be determined for subjects who were administered the IMP.

8 Description of Analysis Datasets

The safety analysis set will be used in the statistical analyses. The following analyses will be performed by cohort and overall (Cohorts 1, 2, and 4).

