9.3.7 Chest X-ray

The following item will be tabulated using the normality judgment (normal or abnormal) for the chest x-ray at each time point.

- Shift table from baseline

10 Efficacy Analysis

The efficacy analysis set will be used in efficacy analyses. The following analyses will be performed by cohort and overall (Cohorts 1, 2, and 4).

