10.3 Overall Survival

The following analysis will be conducted by cohort and overall (Cohorts 1, 2, and 4) in the efficacy analysis set. Also, same analysis will be conducted for responders, non-responders, and overall in efficacy analysis set. Responders will be defined as those subjects who meet the criteria of overall remission.

- Kaplan–Meier plots with median survival time

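### The efficacy set depends on undefined post-dose efficacy data; if a response assessment is required, early losses leave the remission denominators and nonzero rates can only rise

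*SAP*

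**What the plan says.** Protocol 11.1.2 and SAP 5.1.2 define the efficacy set identically. A subject must have been dosed and must also "have data of the efficacy endpoints after the start of IMP administration". The safety set (SAP 5.1.1) asks only for a dose.

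The efficacy set governs every efficacy result. SAP section 10 opens with "The efficacy analysis set will be used in efficacy analyses", and SAP 10.3 says of overall survival (OS): "The following analysis will be conducted by cohort and overall (Cohorts 1, 2, and 4) in the efficacy analysis set".

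Several other provisions bear on who has such data:

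- Protocol 3.3.2 lists "overall survival, and composite complete remission duration" as efficacy endpoints beside the three remission rates.
- Protocol 11.2 states that "all deaths (regardless of cause) will be defined as events". SAP 6.2.7 adds: "Survival time will be censored on the last date of survival confirmation if a subject is alive or lost to follow-up".
- Protocol 7.2.3.2 plans collection for everyone: "The survival of each subject will be investigated at the end of the primary evaluation part of the trial".
- Protocol 7.2.3.1 has a course without a marrow examination recorded as NE, and clear progression without prior remission recorded as progressive disease. SAP 10.1 tabulates both.
- SAP 6.4 rules out imputation.

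No provision says that NE or unassessed subjects stay in the denominators of the best-response rates.

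**The concern.** Membership of the set turns on what happens after dosing, and the deciding words are left open. They do not say data on any efficacy endpoint, nor do they say a response assessment.

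In Course 1, the schedule of events places efficacy evaluation on Day 29 and at the withdrawal examination. Under Protocol 7.1.5, marrow is taken at withdrawal only if blood counts suggest remission or progression is clear. After a serious adverse event or progression, only the feasible tests are done. A dosed subject with no response assessment is therefore most likely an early death or an early withdrawal.

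If such subjects are removed, the remission rates describe those who lasted long enough to be assessed. With three to six subjects per cohort, one removal is visible. No intervals are planned (SAP 6.5), so the reader sees only the shifted point estimate. SAP section 4 also has the included subjects confirmed shortly before the final analysis. In an open-label trial, the clause could then be interpreted when responses are already known.

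**Working it through.** **Plan's own figure.** The cohort maxima in Protocol 3.4 give 6 + 6 + 6 + 6 = 24, the stated maximum. The pooled group (Cohorts 1, 2 and 4) is at most 6 + 6 + 6 = 18. There is no power calculation to reproduce.

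**Step 1: two readings of the clause.**

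- *Broad reading (data on any efficacy endpoint).* OS is an efficacy endpoint, so a death after dosing supplies data. A later survival confirmation or a recorded NE would do so too. The set is then close to all dosed subjects.
- *Narrow reading (a response assessment is needed).* Of n dosed subjects, k without an assessment leave the set.

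**Step 2: direction for remission rates under the narrow reading.** CR, CRp, CRi and PR all need a marrow finding (table in SAP 6.2.5), so none of the k subjects can be among the r remitters. The rate changes from r/n to r/(n − k). This is larger whenever r > 0 and k > 0, and stays at 0% when r = 0.

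| n dosed | r remitters | k = 0 | k = 1 | k = 2 |
|---|---|---|---|---|
| 6 | 1 | 1/6 = 16.7% | 1/5 = 20.0% | 1/4 = 25.0% |
| 6 | 2 | 2/6 = 33.3% | 2/5 = 40.0% | 2/4 = 50.0% |
| 18 | 4 | 4/18 = 22.2% | 4/17 = 23.5% | 4/16 = 25.0% |

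**Step 3: how likely a removal is.** The documents give no early-loss rate, so the per-subject rate q is an assumption, taken from 5% to 20%. The chance of at least one removal in a cohort of six is 1 − (1 − q)^6:

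- q = 5%: 26.5%
- q = 10%: 46.9%
- q = 20%: 73.8%

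For rough context, fatal serious adverse events in the earlier study were 14/216 = 6.5% (phase 2) and 17/93 = 18.3% (phase 1), from Protocol 1.2.2.1.1. Those figures cover that study's whole reporting period, not one course.

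**Step 4: average shift.** If all lost subjects are non-remitters, an all-dosed rate p is reported as about p/(1 − q). With p = 8/50 = 16%, the earlier study's figure for relapsed or refractory AML, this gives 0.16/0.95 = 16.8% at q = 5% and 0.16/0.80 = 20.0% at q = 20%.

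**Step 5: OS under the narrow reading.** The direction is not fixed.

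- Drop the only early death from six: survival just after that time changes from 5/6 = 83.3% to 100%.
- Take deaths at months 1 to 5 and a sixth subject alive at month 12, and drop the sixth for want of a response assessment: survival after the first death changes from 5/6 = 83.3% to 4/5 = 80.0%.
- Drop a subject censored before any death: the curve does not change.

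**The case against.** The strongest reply is that the plan's text mostly keeps early failures in. OS is one of the efficacy endpoints, every death is an event, survival is to be investigated for each subject, and living or lost subjects are censored, not discarded. Efficacy is also evaluated at withdrawal, progression and NE are recorded results, and best overall response is to be documented for each subject at completion or withdrawal. Course 1 is inpatient, so a dosed subject with no endpoint data at all should be rare. This stands as an argument for the broad reading, but nothing in either document adopts that reading. Tabulating NE by course also does not settle who is counted in the best-response rates.

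Three stronger inferences are tempting and are not supported:

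- *Early deaths are excluded from OS.* That needs a response-assessment condition which neither document states.
- *Any bias in the Kaplan-Meier curve is favourable.* Step 5 shows that dropping a long survivor lowers it.
- *The plan expects efficacy exclusions,* because SAP 7.2 says "The frequency distribution of subjects included or excluded in each analysis set will be determined". That table covers every set, including the DLT, PK and PD sets, which have their own conditions beyond dosing. It would disclose any exclusion, which helps the reader, but a disclosed count does not correct a rate.

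**Conclusion.** The point holds as a defect in the set definition with one certain direction: under the narrow reading, nonzero remission rates can only rise. The shift is about 7 percentage points for one removal from a cohort of six with two remitters (33.3% to 40.0%), and about 3 points for two removals from 18 with four remitters (22.2% to 25.0%). These counts are illustrations, and the removal probabilities rest on the assumed loss rates. Under the broad reading, the clause changes almost nothing. For OS, the documents support only that membership is unclear and that the effect could go either way.

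The consequence is limited. Efficacy is secondary and descriptive, no test is planned, and the primary DLT analysis uses a different set. It is still worth changing, because the clause is a stated membership rule that depends on outcome, and on neither reading does it serve a purpose.

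**What to change.** In Protocol 11.1.2 and SAP 5.1.2, define the efficacy set as all subjects who received one or more doses. In SAP 10.1, state that NE or the absence of any post-dose assessment counts as non-remission in the complete, composite complete and overall remission rates, with NE still shown as its own category. In SAP 10.3, state that every dosed subject enters OS from first dose, censored as SAP 6.2.7 already provides, and that unassessed subjects belong with the non-responders in the responder split. If only the SAP is revised, list the change in SAP section 13.

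This needs no new data and no change to the planned 24 subjects. The cost is a few sentences, and reported remission rates may be slightly lower.
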